## **Study Size**

The implementation of the RTS,S/AS01 vaccine will use the EPI, building on routine systems. The evaluation period is the time needed to monitor a sufficient number of children for vaccine safety, impact and feasibility. The evaluation of mortality drives the overall scale of the Malaria Vaccine Pilot Evaluation. In order to detect in each country a 10% decrease in all-cause mortality in vaccine-eligible children, and assuming a minimum mortality risk of 25 per 1000 in the target age group, a total of 60 areas each contributing approximately 4,000 children per year to the evaluation, and evenly split between implementation and comparison areas, will be required. Country-specific protocols will include updated sample size estimates, based on cluster size and local mortality estimates, and

are expected to require a range of 46-60 areas per country. Each year this will generate a total of approximately 120,000 children in the implementation areas and 120,000 children in the comparison areas in each country.

Hospital-based safety surveillance will be nested within parts of the MVPE area and include up to 8 hospitals per country, serving up to 24 areas across the Programme. This is designed to enable detection, with 90% power, of a 2.6-fold increase in the risk of meningitis and an 1.7-fold increase in the risk of cerebral malaria in children living in areas where RTS,S/AS01 is introduced. In addition, all health care facilities in the study areas will be supported to identify and report AEFI and VRs will identify non-hospitalized deaths. All AEFI and deaths will have their relationship with immunisation status evaluated.

A representative sample of 100 households per cluster (up to 6,000 households per country) will be surveyed to estimate the coverage of vaccinations in both implementation and comparison areas with a precision of +/- 2% in each of the three countries.

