Areas will be defined according to the size of the birth cohort, aiming for an annual birth cohort of 4,000 children. Feasibility will be evaluated in the context of routine ongoing RTS,S/AS01 vaccination. Figure 3 illustrates that a minimum of 30 months of routine vaccination will be required to provide sufficient observation time to assess the feasibility of providing the fourth dose to children receiving their first dose in the first year of the programme (dark green in figure 3). All children receiving any doses of RTS,S/AS01 in the 30 month window (light green in figure 3) will contribute to the evaluation of safety and impact.

Figure 3: Overview of children contributing to feasibility, safety and impact evaluations

\* To be decided by authorities of pilot countries

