#### 9.2.2 Community-based surveillance

The majority of deaths in many sub-Saharan countries occur in the community, rather than in hospitals or health facilities. The evaluation of the impact of RTS,S/AS01 on survival will therefore require the development and consolidation of community-based systems to document and report deaths. Experience from the INDEPTH network of demographic surveillance systems (DSS) has confirmed the feasibility of recruiting and training a cadre of village-based reporters (VRs). Their role is to identify and document deaths occurring in their village and any surrounding area assigned to the VR. Deaths may be identified either through (i) door-to-door visits of each household in the VR's assigned area, in which case there will be approximately 131 VRs per cluster, employed full time and each expected to visit around 150 households every 3 months, or (ii) by VRs being notified of any key events by a specially developed local network of informants, in which case there would be around 25 VRs per cluster, each VR capturing information from around 800 households. The MVPE will build on relevant existing and developing capacities and systems to generate key vital event data for the evaluation and do so with the aim of strengthening sustainably the local capacity for vital event monitoring.

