### 11.2.2 Survey population

Surveys will be carried out in a sample of households from implementation and comparison areas. Four groups of ~25 households (survey "clusters" or primary sampling units, PSUs) will be selected from each implementation and comparison cluster, such that each household in a PSU has an equal probability of being included in the sample. New samples of households will be drawn for each of the surveys. The same sampling methods as used in standardised national surveys (DHS, MIS, MICS) will be used to enhance comparability of the findings and interpretation of the external validity of the evaluation of the RTS,S/AS01 pilot implementation.

The surveys will include a representative sample of households. A typical approach would be a two-stage cluster design as described below, but this may be varied or adapted, provided a probability sampling approach is used.

In the first stage, enumeration areas (EAs) are selected with probability of selection proportional to the estimated population size of the EA. Shortly before the survey, a mapping team will visit the EA and identify all households in the EA. A household will be defined as a group of people who eat meals together and/or who acknowledge the same individual as head of their household. This list of households will serve as the sampling frame for that EA. Mapping teams may record whether any children <5 years of age live in each household, and the sampling frame could then draw only from those houses with the target population. In the second stage of the cluster design, a fixed number of households are systematically or randomly selected from the sampling frame ensuring that each household has an equal probability of selection. The selection of households will occur before the survey team visits the EA to ensure an unbiased sample. On the day of the survey, interviewers visit each of the selected households and question the primary caretakers of all children under 5 years of age. All eligible children in a household should be included. If any primary caretakers of eligible children or the eligible children themselves are not present at the first visit, a revisit will be planned. To minimize the introduction of bias, no substitute household will be included if the owner is repeatedly absent or does not wish to participate to ensure the

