## 11.5 Study size

A sample size of 100 houses per cluster will estimate the cluster-specific coverage of RTS,S/AS01 to within 10% (i.e. 95% CI from 40 to 60%) using a conservative estimate of 50% coverage and a high response rate above 95% in each cluster. Assuming a design effect of 1.5 between clusters, the overall precision in RTS,S/AS01 and coverage estimates of other vaccines over the pilot programme's implementation and comparison areas will be 2% (i.e. 95%CI 48% to 52%) in each country. The second household survey may be powered to generate coverage estimates in the evaluation vs. comparator areas, rather than in each cluster, to within  $\pm 2\%$  of the true value.

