The MVPE will determine whether the introduction of RTS,S/AS01 leads to a reduction in child deaths, and a reduction in the incidence of hospital admission with severe malaria, over the 4 years of the implementation programme (MVIP, Malaria Vaccine Implementation Programme). The MVPE also addresses three safety signals that were observed in the phase 3 trial but whose significance was unclear: an unexplained excess of meningitis cases in RTS,S/AS01 recipients, an excess in cerebral malaria cases among RTS,S/AS01 recipients who developed severe malaria and, among the relatively small number of deaths that occurred in the trial, an excess of deaths among girls who received RTS,S/AS01 compared to girls who did not receive RTS,S/AS01. The data to be collected

¹ In the phase 3 trial, for every 1000 children vaccinated with 4 doses, a total of 1774 (95% CI 1387–2186) cases of malaria, 40 (95% CI 19–64) hospital admissions due to malaria, and 19 (95% CI 4 to 35) cases of severe malaria, were averted over about 4 years.

over 4 years will inform a policy decision about wider use of RTS,S/AS01 as a means to reduce malaria morbidity and mortality, when provided in addition to existing malaria control measures. It is anticipated that sufficient data to assess the safety signals are likely to be available after the first 2 years of the evaluation. At that time, all available data would be reviewed, including outcomes related to safety of the vaccine in routine use (meningitis, cerebral malaria, mortality by gender, AEFI), the impact on severe malaria and all-cause mortality, coverage of the first 3 doses, preliminary data on administration of the 4th dose, and cost-effectiveness assessment. A recommendation about wider use of the vaccine might therefore be made before final impact data are available, recognizing that the impact in any setting will depend on coverage and timeliness of vaccination and the malaria burden, which may differ from those in the MVIP [3].

2. Design of the evaluation

A total of 158 clusters, 66 in Ghana, 46 in Malawi and 46 in western Kenya, each cluster with a total population of about 100,000 on average, were randomized to either introduce RTS,S/AS01 vaccine in 2019 or to delay introduction until a decision is reached about safety and effectiveness.

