Table 1: Number of clusters randomized in each country, number of surveillance hospitals, and the number of clusters within the catchment of the sentinel hospitals

Country	Clusters	Population: annual birth cohort mean (range)	Sentinel Hospitals	Clusters in sentinel hospital catchments	Catchment clusters: annual birth cohort mean (range)
Ghana	66	3975 (912,8954)	8	32	4628 (1202,8954)
Kenya	46	5488 (2702,10739)	6	28	5559 (3487,10739)
Malawi	46	4820 (2816,8112)	4	17	5115 (2816,8112)
TOTAL	158	4661	18	77	5074

(excludes areas where the GSK phase 4 study is being done in each country)

Hospital and mortality surveillance will start when RTS,S/AS01 vaccination begins, or as soon as possible after that date, and be maintained until 46 months from the start of RTS,S/AS01 vaccination.

Administration of doses of RTS,S/AS01 and of other vaccines will be recorded by the EPI programme in each country using their normal record keeping system. Vaccination coverage will also be measured independently through community surveys. A survey will be undertaken at baseline, to measure coverage of EPI vaccines and Vitamin A, deworming treatment, malnutrition by MUAC, and the prevalence of *P.falciparum* infection (using an HRP2 Rapid Diagnostic Test). A second survey will be undertaken after about 18 months to measure coverage of EPI vaccines and, in RTS,S clusters, coverage of 1,2 and 3 doses of RTS,S in children 12-23 months of age. A third survey is planned to measure coverage of the fourth dose of RTS,S.

The MVPE was designed to detect differences in disease and mortality rates, over 46 months, between RTS,S and comparison clusters. Specifically, it was powered to detect a reduction in all-cause mortality in each country in RTS,S clusters of 10% or more (with 90% power) ; to detect a 2.6-fold or greater increase in the rate of meningitis (all countries combined) with 90% power ; to detect an increased incidence of cerebral malaria if the true rate is increased by 1.7-fold or more; and to detect an increase in the female:male mortality ratio with 90% power if the ratio is increased by 1.15-fold or more.

3. Description of the clusters

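### The household-survey precision in Protocol 11.5 counts each sampled house as one target-age child; without an age screen, RTS,S coverage is known to about ±4 to ±5 points per country, not ±2

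*Protocol*

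**What the plan says.** Protocol 11.5 states that "A sample size of 100 houses per cluster will estimate the cluster-specific coverage of RTS,S/AS01 to within 10" percentage points, assuming 50% coverage and response above 95%. With a design effect of 1.5 it then gives ±2 points for each country. The abstract (section 4, Study Size) repeats the claim for up to 6,000 households per country: "with a precision of +/- 2% in each of the three countries".

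The primary feasibility objectives (8.5.1) concern two one-year age bands in each country: three doses by 12 months among children aged 12-23 months, and the fourth dose by 27 months among children aged 27-38 months. Under 11.2.1, RTS,S coverage is measured in intervention areas only.

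On sampling, 11.2.2 takes four groups of about 25 households per cluster, such that "each household in a PSU has an equal probability of being included in the sample". It adds that mapping teams may record whether a household has any child under 5, and that "the sampling frame could then draw only from those houses with the target population".

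Section 11.5 ends by allowing the second survey to be powered by arm, to within ±2%, instead of per cluster. SAP section 17 describes the midline survey population as children aged 12-23 months. Neither gives a frame or a number of children.

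**The concern.** The unit of analysis is a child in a twelve-month age band, but the calculation is in houses. Section 11.5 has no term for target-age children per house, and most households have no child in a given one-year band. If the sample is drawn as 11.2.2 describes, the number of children behind each coverage estimate is a fraction of the number of houses visited.

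At stake is the stated precision of the primary quantitative feasibility outcome. The protocol sets no coverage threshold, so no changed decision is claimed. Cluster-specific coverage is not a primary objective; its ±10 matters only because the plan states it.

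**Working it through.** **Formula.** Half-width in points = 196 × √(deff × p(1−p)/n), with p = 0.5.

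**Reproducing the plan's figures**
- Per cluster, deff 1: n = 100 gives 9.8; n = 95 gives 10.1. This matches ±10.
- Per country, deff 1.5, 30 implementation clusters × 100: n = 3,000 gives 2.2. Both arms, n = 6,000, gives 1.55. Either rounds to ±2.

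Both results need n, the number of children, to equal the number of houses.

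**Target-age children per 100 unscreened houses**
- Households per cluster, from the two staffing options in Protocol 9.2.2: 131 × 150 = 19,650; and for the second option, "in which case there would be around 25 VRs per cluster, each VR capturing information from around 800 households", 25 × 800 = 20,000.
- Births per cluster per year: Protocol 7.6.5 is "aiming for an annual birth cohort of 4,000 children"; SAP Table 1 gives means of 3,975 (Ghana), 4,820 (Malawi) and 5,488 (Kenya).
- Yield = 100 × births / 20,000: 20.0 at the planning value; 19.9, 24.1 and 27.4 for the three countries. Deaths before the target age are ignored, which slightly favours the plan.

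**Cross-check without the staffing figures.** SAP section 2 describes "46 in Malawi and 46 in western Kenya, each cluster with a total population of about 100,000 on average". With 4,000 to 4,661 births per year (4,661 is the overall mean in SAP Table 1) and an assumed 4 to 6 people per house, 100 houses (400 to 600 people) hold 16 to 28 such children. One child per house would need 100,000/4,661 = 21.5 to 100,000/4,000 = 25 people per house.

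**Precision with these yields** (95% response, implementation clusters only, taken as half of the 66, 46 and 46 clusters)

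| | Clusters | Children per cluster | Per cluster, deff 1 | Children per country | Per country, deff 1.5 | Per country, lower deff |
|---|---|---|---|---|---|---|
| Ghana | 33 | 18.9 | ±22.6 | 623 | ±4.8 | ±4.1 (deff 1.08) |
| Malawi | 23 | 22.9 | ±20.5 | 527 | ±5.2 | ±4.5 (deff 1.10) |
| Kenya | 23 | 26.1 | ±19.2 | 600 | ±4.9 | ±4.2 (deff 1.115) |

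The lower design effect assumes that 1.5 was meant for 25 children per sampling unit. Then ICC = 0.5/24 = 0.021, and deff = 1 + (m − 1) × 0.021 with m of about 5 to 6.5 children per unit. The per-cluster figures carry no within-cluster design effect.

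Holding ±2 at deff 1.5 needs 1.5 × 0.25 × (1.96/0.02)² ≈ 3,600 target-age children in implementation clusters.

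**With screening** (95% response)
- Under-5 screen, assuming 50% to 70% of households qualify: 20/0.5 = 40 to 20/0.7 = 28.6 target-age children per 100 houses. Per cluster this gives ±16 to ±19. With 30 clusters, n = 1,140 to 814 gives ±3.5 to ±4.2 at deff 1.5, or ±3.1 to ±3.6 with the lower deff.
- Exact age-band screen, deff 1.5: 30 clusters, n = 2,850, ±2.2; 23 clusters, n = 2,185, ±2.6.
- Exact-band screen with the 100 houses divided equally between two bands: n = 1,425 gives ±3.2; n = 1,092 gives ±3.6. Houses with a child in each band would improve this somewhat.

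**The case against.** The strongest reply is that 11.5 never says a house equals a child, and 11.2.2 contains a design under which its figures hold: a frame limited to houses with the target population. The two-stage scheme is called typical and may be adapted, so an unscreened frame is no more mandatory than a screened one. The second survey may also be sized separately by arm and limited to children aged 12-23 months, which SAP section 17 takes up for the midline.

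This narrows the point without removing it. The screen is optional, the item recorded on the listing is any child under 5, and 11.5 does not invoke it. The sentence on powering the second survey and the midline age range supply neither a frame nor a sample size. They do make the gap more easily closed for dose 3 than for dose 4.

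Some inputs are also unfavourable to the plan, and these points stand:
- Keeping deff 1.5 with few children per sampling unit is pessimistic, so the lower-deff column belongs beside it.
- SAP Table 4 reports 73.7% administrative dose-1 coverage. At that level half-widths shrink by about 12% (√(0.737 × 0.263/0.25) = 0.88), to about ±3.6 to ±4.6. The plan's own figure shrinks by the same factor, so the ratio is unchanged.
- The 20,000 households are a staffing approximation, and the Malawi and Kenya yields pair it with later birth figures.

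Reading ±2 as pooled over both arms does not help. RTS,S coverage is measured in one arm, and for other vaccines 60 clusters × 20 to 27 children (n = 1,200 to 1,620) give ±3.5 to ±3.0 at deff 1.5.

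**Conclusion.** The concern holds. As written, section 11.5 and the abstract claim a precision that the household sample in 11.2.2 does not deliver. For RTS,S coverage in implementation clusters, the half-width is about ±4.1 to ±5.2 points per country, roughly double the stated ±2, and about ±19 to ±23 per cluster against ±10. An under-5 screen leaves about ±3 to ±4 per country; only a screen on the exact one-year band brings back about ±2.2 to ±2.6.

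The result rests on about 20,000 households per cluster, the stated birth cohorts, 50% coverage, 95% response and an even split of clusters. Intervals computed under 11.7 would still be valid because they would use the children actually observed. The fault lies in the planned precision, and the change should be made.

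**What to change.** In section 11.5 and the abstract:
- State the frame for each survey and the expected number of target-age children per 100 houses.
- Restate RTS,S precision for implementation clusters only, separately for 12-23 and 27-38 months.
- Drop or correct the ±10 cluster-specific figure.

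This is a wording change and adds no interviews.

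If about ±2 is to be kept, record child age on the household listing already planned and draw from households with a child in the target band. Use a separate or larger sample when two bands are measured in one survey, as at month 30. Keep the general household frame for the secondary objectives that need it, such as net use and care-seeking. The cost is an added item on the listing form, about 25/0.274 = 91 to 25/0.20 = 125 households listed per sampling unit to find 25 eligible ones, and more interviews at month 30. Enumeration-area size is not given, so whether that listing is feasible cannot be confirmed from the documents.

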## 11.6 Data management

Data will be captured electronically according to the standard approach in each country. Details of the system will be agreed with the research partners and presented in country-specific protocols. Information from the different countries will be harmonized and compiled into a single database.

## 11.7 Data analysis

The prevalence and corresponding 95% confidence intervals will be estimated for the different indicators, taking into account the clustered nature of the survey data. Descriptive statistics will describe the timeliness of vaccinations and breakdown key indicators (e.g., vaccine coverage) by gender. Comparison of the indicators between implementation and comparison areas will be based on the confidence intervals.

## 11.8 Quality control

Standard approaches to quality control will be implemented as is usually done by the DHS, MIS and/or MICS programmes in each country. Repeat and accompanied household interviews (as described in section 9.8), including in relation to the selection of households in the community, and in conjunction with internal consistency and logic checks of survey question responses, will assure the quality of household survey data. The CRO will review a 5% sample of informed consent forms.

## 11.9 Limitation of the research methods

Accepted approaches to selection of a representative sample of households will be used. Nevertheless, given the necessarily low household sampling fraction, it is possible that inaccurate estimates of the various parameters may be generated within individual clusters. This risk is ameliorated by the number of areas included in the pilot programme which should ensure overall robust parameter estimates in the evaluation and comparator areas.

## 11.10 Other aspects

None

# 12 Protection of human subjects

## 12.1 Regulatory and ethical considerations, including the informed consent process

The evaluation will be conducted in accordance with all applicable study participant privacy requirements and the guiding principles of the Declaration of Helsinki.

WHO will obtain favourable opinion/approval to conduct the evaluation prior to a site initiating study-related activities in any country, according to local requirements, or will document that neither a favourable opinion nor an approval to conduct the study is needed.

Implementation of the vaccine will be done by the Ministry of Health. Consent for administration of the vaccine will be implied by carers bringing their children to vaccination clinics and accepting the malaria vaccine. Individual written informed consent will not be sought for the administration of RTS,S/AS01 as (a) this is not standard practice when a new licensed vaccine is introduced; (b) the scale of the programme would make quality assurance of formal informed consent difficult to assure; and (c) the process of seeking consent would detract from the real-life nature of the programme and likely undermine the evaluation of feasibility and, as a result, impact. Signed consent will be sought from a parent or legal guardian of children who participate in household surveys, for verbal autopsies, and for the use of hospital data for research.

This master protocol will be submitted to the EMA, WHO and relevant national and institutional review boards to seek approval of the overall design of the evaluation. The WHO review board is guided by the CIOMS guidelines. The national review boards adheres to the protocol and all applicable local regulations.

Detailed country-specific protocols will be developed, including details of when and how informed consent will be sought, and submitted for review to the same ethics committees which review this master protocol. Informed consent forms will be modelled on standard forms for the conduct of verbal autopsies (Annex 14), the capture of non-routine data in hospitals and associated sample storage and processing (Annex 15), and for the household surveys (Annex 16).

Following the joint ethical review, WHO will prepare model ICFs for the various consent-requiring activities. These will embody the applicable ICH GCP or other applicable guidelines. While it is strongly recommended that this model ICF be followed as closely as possible, the informed consent requirements in the model consent are not intended to prevent inclusion of any local requirements. Clinical judgement, local regulations and requirements will guide the final structure and content of the local version of the ICF.

The in-country lead investigator has the final responsibility for the final presentation of the ICF, respecting the mandatory requirements of local regulations. The ICF generated and used by the investigators must be acceptable to WHO and approved (along with the protocol, and any other necessary documentation) by the relevant IRB/IECs.

Standard approaches will be taken to ensure the confidentiality and security of the data collected as part of this evaluation.

Where formal informed consent is required, freely given, written or witnessed/ thumbprinted informed consent will be obtained from each study participant's parent(s)/LAR(s) or an impartial witness, as locally appropriate, prior to participation in the relevant evaluation component.

During household surveys, written/thumb-printed and witnessed informed consent will be sought from the heads of households, with verbal consent sought from the carers of children in the target age range for the evaluation.

The development of village-based mortality surveillance will only proceed with the approval of the locally-relevant community and associated administrative organisations. Before a verbal autopsy is attempted, written/thumb-printed and witnessed informed consent will be sought from parents/carers of children who have died in the eligible age range.

Assessments of safety in sentinel hospitals will be based on recommended medical practise. As such, written informed consent will not be requested for the collection of blood or CSF samples for routine investigation. However written/thumb-printed and witnessed informed consent will be sought from parents/carers of children before their samples are subject to additional laboratory investigation or longer term storage.

